#### 9.7.1.2 Primary Analysis

All protocol-specified data analysis will be conducted by the CRO (IQVIA). The primary analysis will be conducted **at the end of the data collection period**.

### 9.7.2 Planned Method of Analysis

#### 9.7.2.1 General Considerations

Categorical variables will be presented as counts and percentages of the total. Continuous variables will be described using the mean, standard deviation, median, first quartile, third quartile, minimum and maximum. Point estimates will be accompanied by 95% CIs.

#### 9.7.2.2 Missing or Incomplete Data and Lost to Follow-up

No imputation method will be used for missing data. Patients with missing age, **sex**, information about malignancy diagnosis, ESA treatment (start date), chemotherapy treatment, and Hb value recorded at baseline will be excluded during the selection procedure (see Section 9.2.3.1).

For the other variables, missingness will be quantified and reported as the number and percentage of missing observations for each variable.

### **9.7.2.3 Descriptive Analysis**

#### **9.7.2.3.1 Description of Study Enrolment**

Study enrolment will be tabulated by country, by type of primary tumour, and by type of ESA.

#### **9.7.2.3.2 Description of Subject/Patient Characteristics**

Patient demographics (age, sex), clinical characteristics (malignancy characteristics, type of chemotherapy treatment received, presence of comorbidities and previous receipt of RBC transfusions), type of ESA, and country will be summarized with descriptive statistics overall and by ESA type, where appropriate.

#### **9.7.2.4 Analysis of the Primary, Secondary, and Exploratory Endpoint(s)**

##### Primary endpoint

The number and proportion (%) of patients receiving myelosuppressive chemotherapy with a baseline Hb level of  $\leq 10$  g/dL (as per SmPC), and  $\leq 11$  g/dL (as per Study 20070782) prior to or at initiation of ESA treatment will be summarised with descriptive statistics overall and stratified by ESA type, type of malignancy, and country.

The variable will be expressed both as continuous (mean, SD, median, min and max) and categorical ( $\leq 10$  g/dL vs  $> 10$  g/dL and  $\leq 11$  g/dL vs  $> 11$  g/dL), in accordance with **the** SmPC and Study 20070782 categorization.

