Baseline Hb level at ESA initiation is considered an important determinant of safety outcomes during chemotherapy treatment, including mortality, tumour progression, and thrombotic events. The most recent Cochrane review of the use of ESAs for patients with cancer, found that overall survival was shorter and on-study mortality was higher in subjects initiated on an ESA in comparison to those who were not initiated on an ESA who had a baseline Hb level of > 12 g/dL, but not in those with a baseline Hb of < 10 g/dL or 10 to 12 g/dL (Tonia et al, 2012). Study 20070782 was a phase 3 randomised, controlled study that investigated darbepoetin alfa vs placebo in NSCLC subjects receiving chemotherapy, designed to address the potential risk of increased mortality and adverse tumour outcomes with ESAs in the oncology setting. The study reached its primary and secondary endpoints of non-inferiority for overall survival (OS) and progression-free survival (PFS) over placebo. The baseline Hb level at darbepoetin alfa initiation was < 11 g/dL in 96% of subjects and was < 10 g/dL in 52% of subjects.

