#### 9.3.2 Outcome Assessment

##### Primary outcome

The most proximal Hb value within 4 weeks preceding (and including) the date of first ESA administration will be used to define the Hb level at index. The proportion of patients with the Hb value at index  $\leq 10\text{g/dL}$  (as per SmPC), and  $\leq 11\text{ g/dL}$  (as per Study 20070782) is the primary outcome.

There is no pre-specified threshold for determining an acceptable minimal clinical difference between Study 20080782 and this study. The results will be contextualized against Study 20070782 and other literature on ESA use.

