### 9.5 Study Size

The planned sample size is estimated at 1625 patients who received an ESA during myelosuppressive chemotherapy, and at an estimated **24** study sites across the **6** countries. Recruitment will be competitive, with no limit on the number of **sites activated per country, or** patients recruited per site, country, or year, however patient recruitment will be reviewed regularly to minimise recruitment bias. Characteristics of recruited patients will regularly be compared, where data allows, against non-recruited site data, or published regional, and national data. Comparisons will include the distribution of cancer diagnoses and sociodemographic characteristics. The number of patients approached compared to the number consented per site will be regularly reviewed. The distribution of recruitment within and between countries will also be regularly reviewed. Where discrepancies arise, assertive outreach to site and country investigators will aim to encourage widened recruitment and site selection. Previous

European prospective studies describing Hb levels in patients receiving darbepoetin alfa and other ESAs enrolled between 150 and 1,800 patients (Aerts et al, 2012, Smakal et al, 2018, Berbec et al, 2018). In an analysis of patients with solid tumours who received darbepoetin alfa in European clinical practice between 2008 and 2010, darbepoetin alfa was initiated at a Hb level < 10 g/dL in 50% of breast cancer, 57% of CRC, 60% of ovarian, and 57% of lung cancer patients (Aerts et al, 2012). The Hb level at ESA initiation was between 9 and < 11 g/dL in 80% of breast cancer, 76% of CRC, 76% of ovarian, and 77% of lung cancer patients. A study in multiple European countries to evaluate quality of life in CIA patients treated with ESAs between 2011 and 2013 found that baseline Hb was ≤ 10 g/dL in 97% of patients (clinicaltrials.gov a). A study of darbepoetin alfa use for CIA in Central and Eastern Europe between 2012 and 2016 found that 73% had Hb < 10 g/dL at baseline (Smakal, 2018). A study of darbepoetin alfa use for CIA in Romania between 2011 and 2015 found that 81% had Hb between 9 and 11 g/dL at baseline (Berbec et al, 2018).

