The table below provides estimates for the half-width of the 95% CI surrounding a range of proportions (columns) and sample size (rows) expected. One half the width of the 95% CI for proportions is calculated using an exact method proposed by Clopper and Pearson (Clopper and Pearson, 1934). The sample size is expected to provide adequate precision for estimation of the primary objective, but not for comparisons between initiation groups.

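### Baseline Hb is cut at ≤ 10 and ≤ 11 g/dL, but the Study 20070782 results it will be read against are for < 10 and < 11; starts above 12 g/dL are not shown separately

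*Protocol*

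**What the plan says.** Section 9.7.2.4 (Primary endpoint) sets out the baseline Hb summary: "The variable will be expressed both as continuous (mean, SD, median, min and max) and categorical". The categories are ≤ 10 versus > 10 g/dL and ≤ 11 versus > 11 g/dL, said to follow the "SmPC and Study 20070782 categorization". The Abstract and Sections 7.4 and 9.3.2 use the same two cuts.

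Where the cuts come from:
- Section 7.1 gives the label limit for starting treatment as ≤ 10 g/dL.
- The data analysis part of the Abstract describes ≤ 11 g/dL as the inclusion criterion of Study 20070782.

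The external figures:
- For Study 20070782, Section 7.1 reports that baseline Hb "was < 11 g/dL in 96% of subjects and was < 10 g/dL in 52% of subjects". No other baseline result of that trial is given.
- Sections 7.1 and 9.5 cite European studies with 50 to 60% < 10 (four tumour types) and 73% < 10. One study is cited at ≤ 10 (97%), and others by a range of 9 to 11.

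On use of these figures, Section 9.3.2 says: "The results will be contextualized against Study 20070782 and other literature on ESA use". It sets no threshold for a relevant difference.

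On starts at high Hb, Section 7.1 cites a systematic review in which survival was shorter and on-study mortality higher with an ESA among patients "who had a baseline Hb level of > 12 g/dL, but not in those with a baseline Hb of < 10 g/dL". Nor was this seen in the middle band of 10 to 12 g/dL. A > 12 g/dL category appears in Section 9.7.2.4 for Hb during treatment, but not for baseline Hb.

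**The concern.** A patient whose Hb reads exactly 10.0 counts as ≤ 10 here but is left out of the trial's 52%. The same holds at 11.0 and the trial's 96%. If this study's population had exactly the trial's Hb distribution, its reported proportions would still come out higher than the quoted ones, purely because of the inequality sign. The error runs one way: it makes real-world starts look lower in Hb, relative to the trial, than they are.

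The comparison is descriptive, but it has a use. The Abstract and Section 7.2 say that a substantial prevalence of use inconsistent with Study 20070782 may lead to a mortality study. With no threshold set, readers will put the proportions side by side.

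The second matter is separate. The protocol names starts above 12 g/dL as the stratum with worse survival, and the planned baseline table would not give their number.

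**Working it through.** **1. The plan's own precision figures.** Section 9.5 states that "The planned sample size is estimated at 1625 patients" and that the half-widths in Table 1 are "calculated using an exact method proposed by Clopper and Pearson". With x events in n, the limits are the 2.5% quantile of Beta(x, n − x + 1) and the 97.5% quantile of Beta(x + 1, n − x); the half-width is half their difference. Nine cells of Table 1 were recomputed and all agree to six decimals, for example 0.024793 (n = 1600, p = 0.5) and 0.024831 (n = 600, p = 0.9). At n = 1625 the half-width is 2.46 points at p = 0.52 and 0.985 points at p = 0.96.

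**2. What the sign changes.** P(≤ c) − P(< c) is the share of patients recorded at exactly c. It depends on the recording precision and the spread of Hb. The protocol gives neither, so both are assumed below.

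**3. From the trial's two figures, without a distribution.** 96% − 52% = 44% of trial subjects lay from 10 to below 11 g/dL. With one-decimal recording that interval holds ten values (10.0 to 10.9), on average 4.4 points each. If frequency does not rise from 10.0 to 10.9, at least 4.4% were at 10.0, and the trial's 52% would read at least 56.4% on ≤ 10.

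**4. From a normal curve through the same figures.** SD = (11 − 10) / (z(0.96) − z(0.52)) = 1 / (1.751 − 0.050) = 0.588 g/dL. With one-decimal rounding, < 10 means below 9.95, so the mean is 9.95 − 0.050 × 0.588 = 9.92. The share at 10.0 is Φ((10.05 − 9.92)/0.588) − Φ((9.95 − 9.92)/0.588) = 0.067, and 52% would read 58.7%. The share at 11.0 is 1.3 to 1.5 points, depending on whether the curve is fitted with or without the rounding shift. By recording precision:

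| Recorded to | Share at 10 | Share at 11 |
|---|---|---|
| 0.1 g/dL | 6.7 to 6.8 points | 1.3 to 1.5 points |
| 0.05 g/dL | 3.4 points | 0.7 points |
| 0.01 g/dL | 0.7 points | 0.14 to 0.15 points |

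**5. Other spreads and locations** (normal, 0.1 g/dL recording, n = 1625; all but the first two columns in percentage points):

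| Share < 10 | SD, g/dL | Share at 10.0 | Half-width for ≤ 10 | Share at 11.0 | Half-width for ≤ 11 |
|---|---|---|---|---|---|
| 50% | 0.6 | 6.62 | 2.44 | 1.44 | 0.90 |
| 50% | 1.0 | 3.98 | 2.45 | 2.30 | 1.69 |
| 50% | 1.5 | 2.66 | 2.46 | 2.08 | 2.08 |
| 60% | 0.6 | 6.28 | 2.33 | 0.90 | 0.69 |
| 60% | 1.5 | 2.55 | 2.38 | 1.69 | 1.82 |
| 73% | 0.6 | 5.22 | 2.04 | 0.41 | 0.45 |
| 73% | 1.5 | 2.16 | 2.13 | 1.12 | 1.42 |
| 90% | 0.6 | 2.62 | 1.30 | 0.07 | 0.17 |
| 90% | 1.2 | 1.39 | 1.40 | 0.33 | 0.61 |

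At 10 g/dL the shift exceeds the half-width when 50 to 73% are < 10, only narrowly at SD 1.5. It no longer does with 90% < 10 and an SD of 1.2 or more. At 11 g/dL the two are of similar size, and the order changes with the assumptions.

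**6. Starts above 12 g/dL.** On the normal curve of step 4 they would be about 0.03% of patients. With mean 9.7 and SD 1.2 they would be 1 − Φ((12 − 9.7)/1.2) = 2.8%, or 0.028 × 1625 ≈ 45 patients. The planned mean, SD, median, minimum and maximum do not give this count.

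**The case against.** The case for leaving the plan alone has several parts.

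- **The cuts are deliberate.** ≤ 10 is the label limit. ≤ 11 is the trial's stated entry criterion, so that proportion has its own meaning: the share who would have met the trial's Hb requirement. This stands, and both should remain the primary categories. A reader might infer that the sign flatters consistency with the label; it does not, because label and category use the same inequality.
- **The size is not in the documents.** A reader might infer that the shift always exceeds the CI half-width. The documents do not support that: it fails at 0.01 g/dL recording, fails at 10 when most patients start well below 10 and the spread is wide, and is not general at 11. The normal curve is also doubtful for a population selected at ≤ 11. The interval argument in step 3 does not need that curve, though it still needs one-decimal recording and non-rising frequencies.
- **Nothing is formally compared.** The protocol tests no hypothesis, sets no threshold and does not say that the ≤ 10 proportion will be set against 52%. The literature it cites mixes < 10, ≤ 10 and ranges, so one sign cannot fit all of it. This lowers the weight of the point. It does not make a side-by-side reading of unlike proportions correct.
- **The > 12 row is a display detail.** A reader might infer that its absence biases the proportions at 10 and 11; it cannot. The group may be small, and the maximum baseline value is reported. But a maximum is not a count, and the protocol already uses > 12 for on-treatment Hb.

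**Conclusion.** The mismatch is a matter of text and is certain: the primary categories use ≤, and the only Study 20070782 baseline results in the protocol, with most of the cited European 10 g/dL figures, use <. No planned proportion is like-for-like with them.

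Its size is conditional. If Hb is recorded to 0.1 g/dL and roughly normal with an SD of about 0.6 to 1.5 g/dL, it is about 2.6 to 6.7 points at 10 g/dL when 50 to 60% are < 10, against a half-width of about 2.5 points. At 11 g/dL it is uncertain, about 1 to 2 points against a half-width of about 1 to 2. With 0.01 g/dL recording it is negligible at both cuts. It touches only the reading against the trial and the literature, not label consistency.

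The lack of a baseline > 12 g/dL category is a separate reporting gap: it shifts nothing, but it leaves out the group that the rationale singles out. Both are inexpensive improvements rather than flaws in the primary analysis.

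**What to change.** - Keep ≤ 10 and ≤ 11 g/dL as the primary categories.
- For the comparison with Study 20070782 and the cited studies, also report < 10 and < 11 g/dL, or obtain the ≤ 10 and ≤ 11 proportions from the sponsor's own trial data. Say in Section 9.3.2 that each external figure is compared on its own inequality.
- Report baseline Hb as ≤ 10, > 10 to 11, > 11 to 12 and > 12 g/dL, each with a 95% CI.

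The individual baseline Hb value is already collected. The cost is a few table rows, with no new data and no change to the sample size.

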##### Secondary endpoints

The baseline demographic and clinical characteristics of patients initiating treatment with an ESA and receiving myelosuppressive chemotherapy will be described as the number and proportion (%) for categorical variables, or as means, SD, median, min and max for continuous variables, for each of the covariates listed in Section 9.3.3, and stratified by ESA type, type of malignancy, and country.

The frequency of ESA treatment, the number of ESA prescriptions, and the duration of ESA prescriptions will be summarized with descriptive statistics overall and stratified by ESA type, type of malignancy, and country. The number and proportion (%) of patients prescribed an ESA for 3, 4, 6, and 9 weeks will be reported.

The starting dose will be summarized with descriptive statistics by ESA type. The number and proportion (%) of patients with at least 1 dose modification will be reported

overall, and (where available) by type of dose modification (eg, dose reduction, dose escalation, therapy interruption).

The number and proportion (%) of patients with 1 or more repeated Hb measures after baseline will be reported.

Hb values reached at pre-specified time points during treatment (ie, 3 weeks, 4 weeks, 6 weeks, and 9 weeks) will be described.

Hb values during treatment will be described in terms of:

- Mean, standard deviation, median, interquartile range, minimum, maximum values.
- The proportion of patients reaching the target Hb level, expressed as:
  - Below target level ( $\leq 10$  g/dL)
  - Target range ( $> 10$  to  $\leq 12$  g/dL)
  - Above target level ( $> 12$  g/dL)
- The proportion of patients at week 9 who:
  - Had a rise in Hb of more than 2 g/dL in any 4-week period
  - Had a rise in Hb of more than 2 g/dL in any 4-week period that did not have a subsequent ESA dose reduction or therapy interruption

Handling of multiple measurements per patients:

All Hb values as recorded within  $\pm 6$  days around each time point of interest (3, 4, 6, and 9 weeks) will be used to inform on the values to be reported for this study. The mean and median value for each patient will be calculated for each time point. For example, at 3 weeks (day 21), the mean and median of all Hb values recorded in days 15-27 will be calculated.

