Describe the baseline Hb levels at initiation of treatment with ESA in patients receiving myelosuppressive chemotherapy	Hb level in g/dL at initiation of ESA, further categorised in 2 alternative ways, as per product label and clinical trial criteria 
 
• Hb <math>\leq</math> 10 g/dL
 
• Hb <math>\leq</math> 11 g/dL
 

Secondary	
Describe the baseline demographic and clinical characteristics of patients initiating treatment with an ESA and receiving myelosuppressive chemotherapy	Demographic characteristics (age and sex), comorbidities, type of malignancy, type of chemotherapy treatment received, red blood cell (RBC) transfusions
Describe the duration of ESA prescription in subjects receiving myelosuppressive chemotherapy	Average prescription length of ESA, number of patients prescribed ESA at weeks 3, 4, 6, and 9
Describe the dose distribution of treatment with ESA in patients receiving myelosuppressive chemotherapy at (a) first prescription of an ESA and (b) subsequent ESA prescriptions (where available)	Prescribed dose, dose frequency, dose modifications.
Describe Hb levels during treatment with ESA in patients receiving myelosuppressive chemotherapy	Hb level during ESA treatment: 
 
• Below target level (<math>\leq</math> 10 g/dL)
 
• Target range (<math>></math> 10 to <math>\leq</math> 12 g/dL)
 
• Above target level (<math>></math> 12 g/dL)
 

Describe the number of patients with a “rapid” rise in Hb level (considered to be more than 2 g/dL in any 4-week period), and whether patients with a rapid rise in Hb have a subsequent ESA dose reduction or therapy interruption	Change in Hb level during ESA treatment, categorised: 
 
• More than 2 g/dL rise in any 4-week period
 
• More than 2 g/dL rise in any 4-week period that did not have a subsequent ESA dose reduction or therapy interruption
 

- *Hypothesis/Estimation*

This is an estimation study and no hypotheses will be tested.

- *Study Design/Type:*

Retrospective medical chart review.

- *Study Population or Data Resource*

The study will include patients diagnosed with any non-myeloid malignancy who initiate treatment with an ESA while receiving chemotherapy and were not previously treated with an ESA.

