The number and proportion (%) of patients with 1 or more repeated Hb measures after baseline will be reported. The mean, median, minimum and maximum Hb values across all measures available after baseline for each patient will be calculated. The number and proportion (%) of patients with median and maximum Hb levels below the target level ( $\leq 10$  g/dL), in the target range ( $> 10$  to  $\leq 12$  g/dL)

and above the target level (> 12 g/dL) will be reported. Rapid increases in Hb level may increase the risk of thrombotic events. Therefore, the number and proportion (%) of subjects with a rise in Hb level of more than 2 g/dL in any 4-week period will be reported. Guidance from the SmPC is to regularly monitor Hb levels and reduce or interrupt the ESA dose if a rapid increase occurs, therefore the number and proportion (%) of subjects with a rise in Hb level of more than 2 g/dL in any 4-week period that had a subsequent ESA dose reduction or therapy interruption in their medical notes will be reported.

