#### **8.2 Secondary**

- Describe the baseline demographic and clinical characteristics of patients initiating treatment with an ESA and receiving myelosuppressive chemotherapy
- Describe the duration of ESA prescription in subjects receiving myelosuppressive chemotherapy
- Describe the dose distribution of treatment with ESA in patients receiving myelosuppressive chemotherapy at (a) first prescription of an ESA and (b) subsequent ESA prescriptions (where available). Dose will be categorized by long-acting and short-acting ESAs to avoid dose conversion.

- Describe Hb levels during treatment with ESAs in patients receiving myelosuppressive chemotherapy.
- Describe the number of patients with a “rapid” rise in Hb level (considered to be more than 2 g/dL in any 4-week period), and whether patients with a rapid rise in Hb have a subsequent ESA dose reduction or therapy interruption.

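### Action after a rapid Hb rise is reported per patient at week 9, not per rapid riser, and the protocol counts it in two opposite directions

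*Protocol*

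**What the plan says.** Section 8.2 of the protocol states the objective in two parts: how many patients have a rapid rise, and "whether patients with a rapid rise in Hb have a subsequent ESA dose reduction or therapy interruption". The second part is a question about rapid risers. The endpoint table in the Abstract (Section 5) repeats this objective.

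Section 9.7.2.4 (Secondary endpoints) sets out the analysis under a single stem, "The proportion of patients at week 9 who", with two items beneath it:

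- A: "Had a rise in Hb of more than 2 g/dL in any 4-week period"
- B: had a "rise in Hb of more than 2 g/dL in any 4-week period that did not have a subsequent ESA dose reduction" or an interruption of treatment

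The Abstract describes the second item in two ways. Its endpoint table has "More than 2 g/dL rise in any 4-week period that did not have a subsequent ESA dose reduction or therapy interruption", which agrees with item B. Its Data Analysis text has "rise in Hb level of more than 2 g/dL in any 4-week period that had a subsequent ESA dose reduction or therapy interruption", which is the opposite event.

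Three other provisions bear on the point. Section 9.7.2.1 attaches a 95% confidence interval to point estimates. Section 9.7.2.5.1 reports secondary objectives by ESA type, tumour type and country. Section 9.2.6 ends follow-up before week 9 if ESA treatment ends or the patient dies.

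**The concern.** A patient without a rapid rise cannot contribute to item B. On a denominator that is not limited to risers, B therefore mixes two things: how often haemoglobin rises fast, and how prescribers respond when it does. The objective asks only about the second. The Abstract links this measure to the product-label guidance on rapid increases, so it bears on one of the study's stated aims, consistency of use with the label. A small value of B could reflect good follow-through or simply few rises.

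The conflict in direction adds to this. A programmer or report author working from the protocol could tabulate either the acted-on or the not-acted-on patients. On any denominator wider than the risers, those two percentages do not add to 100%, so a mislabelled one would not be obvious.

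The stem also leaves open who the patients at week 9 are. They could be everyone assessed up to week 9, or only those still followed then. The narrower reading drops patients whose ESA treatment ended early.

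**Working it through.** **Inputs from the protocol.** Planned N = 1625 (Section 9.5). Interval method: exact Clopper-Pearson, 95% (Section 9.5). The protocol gives neither a rate of rapid rise nor a share of risers without action. Both are assumed below: rise rates of 10% to 50%, and no-action shares of 20%, 50% and 80%.

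**Check against the plan's own figures.** No figure is given for this endpoint. The interval method was checked on Table 1, taking half-width = (upper limit − lower limit)/2. The cells checked reproduce exactly, for example:

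- n = 40, p = 0.5: 0.161982
- n = 600, p = 0.9: 0.024831
- n = 1600, p = 0.5: 0.024793
- n = 1800, p = 0.9: 0.014136

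**Formulas.** Let D be the common denominator of the two items, R the number with a rapid rise, and U the number of those without subsequent action.

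- Item A = R/D
- Item B = U/D = (R/D) × (U/R), the rise rate times the no-action share
- Share wanted by the objective = U/R = B/A
- Acted-on version over the same D = (R − U)/D = A − B

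**Size of the gap.** Here D = 1625 and about half of risers have no action (assumed):

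| Assumed rise rate | R | U | B = U/1625 | Half-width of B | U/R | Half-width of U/R |
|---|---|---|---|---|---|---|
| 10% | 162 | 81 | 5.0% | 1.1 points | 50.0% | 7.9 points |
| 20% | 325 | 162 | 10.0% | 1.5 points | 49.8% | 5.6 points |
| 30% | 488 | 244 | 15.0% | 1.8 points | 50.0% | 4.5 points |
| 40% | 650 | 325 | 20.0% | 2.0 points | 50.0% | 3.9 points |
| 50% | 812 | 406 | 25.0% | 2.1 points | 50.0% | 3.5 points |

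**B on its own.** A value of B = 10% is compatible with a no-action share of 0.10/0.10 = 100%, 0.10/0.20 = 50%, 0.10/0.30 = 33%, 0.10/0.40 = 25% or 0.10/0.50 = 20%, depending on the rise rate.

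**B together with A.** At a 20% rise rate, 0.100/0.200 = 0.50, which is the conditional share. The same division works in every scenario tried. The interval does not transfer: rescaling the half-width of B gives 1.49/0.20 ≈ 7.5 points, whereas the exact half-width on 325 risers is 5.6 points.

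**Direction.** At a 20% rise rate with 20% of risers not acted on, R = 325 and U = 65. The not-acted-on version is 65/1625 = 4.0%. The acted-on version over the same denominator is (325 − 65)/1625 = 16.0%. At 80% not acted on, the two values swap. They coincide only when exactly half of risers are acted on.

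**The case against.** The strongest reply is that Section 9.7.2.4 already reports the rise itself on the same denominator as the no-action item. Anyone can divide one by the other, overall or within a subgroup, and obtain the share the objective asks for. The acted-on and not-acted-on counts are complements among risers, so each follows from the other by subtraction. A per-patient figure is also a legitimate utilisation measure: it says how common rapid rises without action are among treated patients.

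Much of this stands, and it rules out several stronger readings. A reader might infer that the endpoint cannot answer its objective, that the two directions give unrelated numbers, or that subgroups cannot be compared. None of these holds once both items are printed side by side. A reader might also infer that the denominator is all patients and that most of them have no rapid rise. The stem says patients at week 9, which is ambiguous, and no section gives a rise rate. Nor does the whole Abstract contradict Section 9.7.2.4: only its Data Analysis text does, and that text can itself be read as a proportion among risers.

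The reply does not remove the point. The ratio is not a planned output, and the interval that Section 9.7.2.1 calls for would attach to item B, not to the share the objective asks about. The division also fails if the acted-on count is tabulated under the not-acted-on label. Denominators are often left to the statistical analysis plan. Here, however, the protocol has already fixed a stem that does not match its objective and two opposite events, and any later document would inherit both.

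**Conclusion.** The point holds as a mismatch between objective and reported estimate, together with an internal contradiction on which event is counted. Taken alone, the planned no-action figure understates the no-action share among rapid risers by a factor equal to the rise rate: about 10% instead of about 50% at an assumed 20% rise rate with half of risers not acted on. The correct point estimate is recoverable from the two items. Its confidence interval is not recoverable from the planned one and needs the counts of risers.

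The conflict in wording and the unrestricted stem rest on the text alone. The percentages rest on assumed rise and no-action rates, and on taking all 1625 planned patients as the week-9 set. The consequences are limited to a descriptive secondary endpoint. The change is worth making because it alters the reported estimate and its interval, but the primary outcome and the sample size are unaffected.

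**What to change.** In Section 9.7.2.4:

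1. Keep the rapid-rise item on a defined patient set. State whether patients at week 9 means everyone assessed up to week 9 or only those still followed then, given that Section 9.2.6 lets follow-up end earlier.
2. Replace the second item. Among patients with a rise above 2 g/dL in any 4-week period, report the number and proportion with, and the number and proportion without, a subsequent dose reduction or interruption. Give an exact 95% confidence interval on that denominator, overall and by the subgroups in Section 9.7.2.5.1.
3. Align the Abstract's endpoint table and its Data Analysis text with this one definition.

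The per-patient figure can stay as an additional line if it is labelled as such.

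The cost is wording in the Abstract and Section 9.7.2.4 and one table layout; no new data are needed. The price is a wider interval on the smaller denominator (5.6 points instead of 1.5 in the 20% example), and more so within subgroups. That width is the actual uncertainty about the quantity the objective asks for.
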